5.5. Multiplicity Adjustment

A branched fixed sequence method will be used to control the family-wise type I error rate at 0.05 for testing the primary and key secondary endpoints comparing immediate treatment subjects (pooled low and intermediate doses) with deferred treatment subjects in the expansion phase as illustrated in Figure 3. Alpha of 0.05 will be allocated to the primary endpoint, static perimetry responder by pointwise analysis. If statistically significant, the alpha of 0.05 will be passed down to the first secondary endpoint, V30. If V30 is statistically significant, the alpha of 0.05 will be passed down to the visual mobility assessment. If the visual mobility assessment is statistically significant, MAIA microperimetry and patient report outcome (Impact of Vision Impairment – 'Reading and Accessing Information' domain) will be tested under alpha=0.04 and 0.01, respectively. If one or both endpoints are statistically significant, the remaining alpha will be passed down to test low luminance BCVA, contrast sensitivity and EZ area, conditional on the statistical significance of the prior test. If any of the endpoint(s) are not statistically significant, the allocated alpha for testing cannot be passed and testing will stop after all alpha has been spent.

Figure 3: Illustration of alpha distribution

Key: V30=central 30-degree hill of vision. MAIA =microperimetry

5.6. Exploratory Efficacy Variable(s)

5.6.1. Definition

Status: Approved, Date: 16 November 2021

5.6.2. Analysis Methods

6. SAFETY

The proportion of subjects who experience the primary safety outcome and the corresponding 95% confidence interval (CI) based on the normal approximation with continuity correction will be provided for the immediate treatment subjects and deferred subjects prior to treatment in the safety analysis set. The analysis will be performed by study phase, treatment group and overall. The primary safety outcome for all deferred subjects post-treatment will be tabulated separately. A listing of primary safety outcome events will also be provided.

A similar analysis will also be conducted for dose-limiting events (DLEs) in dose escalation phase.

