5.7 Sample Size

This is a Phase I/II trial to establish safety and assess indicators of potential efficacy of the ATIMP, therefore there is no formal sample size calculation. The trial will enrol up to 71 participants (up to 18 in the dose escalation phase, up to 5 in the dose confirmation in paediatric phase, and up to 48 in the randomised expansion phase), as described in section 4.3.2.2. We estimate that inclusion of up to 53 participants will be sufficient to determine the safety and tolerability of the intervention.

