5.10.3.2 Statistical Methods – Outcomes

The primary outcome is safety of subretinal administration of the ATIMP defined as any of the below occurring during the 9 weeks following administration, at least possibly related to the ATIMP, not surgery alone:

- Reduction in visual acuity by 15 ETDRS letters or more
- Severe unresponsive inflammation (defined below)

- Infective endophthalmitis
- Ocular malignancy
- Grade III or above non-ocular SUSAR (see section 5.11.3)

The number of DLEs at each dose level will be summarised by cohort and overall.

Safety data relating to participants at all dose levels will allow estimation of an upper bound for the true event rate through a 95% confidence interval.

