1.2. Trial Design

This is an open-label, phase I/II dose-escalation trial to determine the safety and efficacy of subretinal administration of the study agent (AAV5-hRKp.RPGR) in subjects with genetically confirmed RPGR-XLRP. As shown in Schema of treatment groups with study phases in Figure 1 and Schema of treatment groups within study phases in Figure 2, MGT-RPGR-009 includes three phases, dose escalation phase in adult RPGR patients, dose confirmation phase in pediatric RPGR patients, and randomized expansion phase in adult RPGR patients.

Figure 1: MGT009 Study Design Schematic

[figure not shown]
[figure not shown]

Figure 2: Schema of treatment groups within study phases

In the dose escalation phase, subjects were administered a single dose of ATIMP in cohorts of 3-4 subjects at a time. Based on a review of safety data, the Independent Data Monitoring Committee (IDMC) made recommendations on whether the dose was to be escalated or whether additional subjects were needed to repeat a dose in the cohort. The IDMC concurred on dosing a pediatric cohort at the intermediate dose prior to moving into the expansion cohort.

After an acceptable safety profile had been established in adults, the IDMC agreed to the sponsor's plan for administering the intermediate and low doses in the expansion phase. In the expansion phase, subjects were randomized to either immediate treatment with the low dose, or immediate treatment with the intermediate dose, or to a 6-month deferred-treatment group to receive either the low dose or the intermediate dose. Subjects in the immediate treatment arm were followed for 12 months before migrating to the long-term extension study, MGT-RPGR-010. Subjects in the deferred treatment arm were followed for at least 6 months before crossing them over to active treatment; at the 12-month time point these subjects also migrated to the long-term follow up study, MGT-RPGR-010. 6-month data from deferred arm during deferred period prior to treatment serves as the concurrent control group.

Adults were defined as subjects aged 16+ in the United Kingdom and aged 18+ in the United States.

Safety and efficacy are assessed for 12 months following the intervention by clinical examination and special investigations according to the schedule in Section 5.6 of the protocol.

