1.3. Statistical Hypotheses for Trial Objectives

1.3.1. Primary Safety Hypothesis

The objective of the dose escalation phase is to estimate the proportion of subjects who experienced the primary safety outcome. No formal hypothesis testing will be conducted.

The primary safety outcome is defined as any of the events delineated below and occurring during the 9 weeks following administration, at least possibly related to the ATIMP, not the surgery alone:

- Reduction in visual acuity by 15 Early Treatment Diabetic Retinopathy Study (ETDRS) letters or more
- Severe unresponsive inflammation (defined in Section 4.2.1 of the protocol)
- Infective endophthalmitis
- Ocular malignancy
- Grade III or above non-ocular suspected unexpected serious adverse reaction (SUSAR) (Protocol MGT009, Section 5.11.3.4.2 Severity or Grading of Adverse Events).

Safety will be assessed for 12 months following ATIMP administration for immediate treatment participants in this study (Protocol MGT009) by study phases (dose escalation, dose confirmation and expansion phases) and overall, comparing with 6 months data in deferred treatment arm prior to treatment. Safety outcome captured in a separate long-term follow-up study (Protocol MGT010) for a further 4 years will be summarized separately.

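### The planned normal-approximation interval for the primary safety outcome puts the zero-event upper limit at 1/(2n), four to seven times below the exact limit

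*SAP*

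**What the plan says.** SAP Section 6 gives the proportion of subjects with the primary safety outcome a "95% confidence interval (CI) based on the normal approximation with continuity correction will be provided". On grouping it says: "The analysis will be performed by study phase, treatment group and overall". For DLEs it adds: "A similar analysis will also be conducted for dose-limiting events (DLEs) in dose escalation phase". It names no exact or score method and no fallback for groups with few or no events.

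Protocol Section 5.10.3.2 states the purpose of the interval: safety data from participants at all dose levels "will allow estimation of an upper bound for the true event rate through a 95% confidence interval".

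The groups are small. Protocol Section 5.7 plans "up to 18 in the dose escalation phase, up to 5 in the dose confirmation in paediatric phase". The randomised expansion adds a maximum of 48. SAP Section 1.2 says of the escalation phase that "subjects were administered a single dose of ATIMP in cohorts of 3-4 subjects at a time". SAP Section 1.4 gives 3 children for the confirmation phase, where the protocol allows 5.

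SAP Section 1.3.1 defines the outcome as any of five listed events "occurring during the 9 weeks following administration, at least possibly related to the ATIMP, not the surgery alone". It plans no hypothesis test on it.

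**The concern.** Safety is the primary objective, and this interval is the only planned statement of uncertainty about it. A normal approximation estimates the standard error from the observed proportion. When no event is seen, that estimate is zero, and the reported upper limit is just the continuity correction. The published bound would then exclude event rates that the data cannot exclude, and the error would be in the reassuring direction. In groups of 3 to 55, zero events is a realistic result for an uncommon outcome. With one or two events the approximation remains poor and gives limits outside the range 0 to 100%.

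**Working it through.** The documents state no safety interval or precision figure, so there is none to reproduce. The SAP's method is applied directly.

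**Group sizes**
- Escalation cohort: 3 at the start. SAP Section 1.2 reports 3 to 4, and Protocol Section 4.3.2.2 allows expansion to 6.
- Paediatric confirmation: up to 5 (Protocol Section 5.7).
- One expansion arm: up to 16. Both immediate arms: 32 (Protocol Section 4.3.2.2.5).
- Escalation phase: up to 18.
- All immediate-treatment participants: 18 + 5 + 32 = 55.

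Apart from the escalation cohort, these are planned maxima, not actual numbers.

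**Formulas**, with x events in n participants and p = x/n
- Planned: p ± [1.96 × √(p(1−p)/n) + 1/(2n)]. At x=0 the square root is 0, so the upper limit is 1/(2n).
- Exact two-sided Clopper-Pearson upper limit at x=0: 1 − 0.025^(1/n).

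For n=16 and x=0, the planned limit is 1/32 = 3.1% and the exact limit is 1 − 0.025^(1/16) = 20.6%.

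**Upper 95% limit with zero events**

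| n | Planned | Exact | Ratio |
|---|---|---|---|
| 3 | 16.7% | 70.8% | 4.2 |
| 4 | 12.5% | 60.2% | 4.8 |
| 5 | 10.0% | 52.2% | 5.2 |
| 6 | 8.3% | 45.9% | 5.5 |
| 16 | 3.1% | 20.6% | 6.6 |
| 18 | 2.8% | 18.5% | 6.7 |
| 32 | 1.6% | 10.9% | 7.0 |
| 55 | 0.9% | 6.5% | 7.1 |

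**Upper 95% limit with one or two events (planned vs exact)**

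| n | 1 event | 2 events |
|---|---|---|
| 16 | 21.2% vs 30.2% | 31.8% vs 38.3% |
| 18 | 18.9% vs 27.3% | 28.4% vs 34.7% |
| 32 | 10.7% vs 16.2% | 16.2% vs 20.8% |
| 55 | 6.3% vs 9.7% | 9.5% vs 12.5% |

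For these groups the exact limit is 1.4 to 1.55 times the planned one with one event, and 1.2 to 1.3 times with two. In the smallest groups the shortfall shrinks or reverses. At n=3 the untruncated planned limits are 103% with one event and 137% with two. At n=5 they are 65.1% vs 71.6% exact with one event, and 92.9% vs 85.3% with two. The planned lower limit is negative with one or two events at every size listed.

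**Chance of seeing no event**, (1 − rate)^n. At an assumed true rate of 5% this is 86% at n=3, 44% at n=16 and 19% at n=32. At 10% and n=16 it is still 18.5%, although the planned limit would then claim at most 3.1%.

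**Coverage of the planned 95% interval** (binomial enumeration, assumed true rates)

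| n | 2% | 5% | 10% | 20% |
|---|---|---|---|---|
| 3 | 100% | 100% | 100% | 48% |
| 16 | 100% | 56% | 81% | 96% |
| 18 | 100% | 60% | 85% | 90% |
| 32 | 48% | 81% | 96% | 96% |
| 55 | 67% | 94% | 92% | 97% |

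Clopper-Pearson coverage is 95.7% to 99.9% in the same cells.

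**Score alternatives**, zero-event upper limit at n=3, 16, 32 and 55: Wilson 56.1%, 19.4%, 10.7% and 6.5%; continuity-corrected Wilson 69.0%, 24.1%, 13.3% and 8.1%.

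**A related row.** SAP Section 6 also asks for this interval in deferred subjects before treatment. The outcome must follow administration, so that row is zero by definition. At n=16 it would show an upper limit of 3.1%, which carries no information.

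**The case against.** The large ratios need zero events, and the documents give no event rate. That is true. With one or two events the gap is much smaller, and in the smallest groups the planned upper limit can exceed the exact one.

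The protocol's upper-bound sentence refers to participants at all dose levels. The comparison closest to it is therefore the pooled one, not a cohort of 3. In absolute terms the pooled gap is smaller, 0.9% vs 6.5%, but it is still seven-fold, and SAP Section 6 does ask for the interval by phase and treatment group.

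The SAP does not use the word Wald. If a continuity-corrected score interval was intended, the zero-event limits are close to or above exact and the problem disappears. But the SAP names no score method, and its wording most naturally describes the simple interval. The programming instructions sit in the Data Presentation Specifications, which were not available. The SAP also cites protocol v12.0, while the amendment log of the protocol supplied ends at v11.0, so the purpose statement could have changed.

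Finally, no test is planned on this outcome, adult escalation is complete, and events will be listed, so a reader can recompute exact limits. This limits the consequence to reporting. It does not make the reported bound correct.

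**Conclusion.** The concern holds. Followed as written, SAP Section 6 gives a zero-event upper limit of 1/(2n), which is 4.2 to 7.1 times below the exact limit for groups of 3 to 55. With one or two events in groups of 16 or more, the exact limit is about 1.2 to 1.55 times the planned one. Actual coverage falls to about half the nominal level in some plausible settings. This defeats the purpose the protocol gives for the interval.

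The conclusion rests on the usual reading of the SAP wording, on planned group sizes, and, for the largest ratios, on no events being seen. For DLEs the method is inferred from the reference to a similar analysis. The point should be fixed before reporting, but it does not affect any test or dose decision in the documents.

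**What to change.** In SAP Section 6, replace the normal approximation with continuity correction by two-sided 95% exact (Clopper-Pearson) intervals, stated for both the primary safety outcome and DLEs. A Wilson score interval would also serve. If a continuity-corrected score interval was meant all along, the SAP should name it.

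In the same edit, one sentence could say that the overall row means all immediate-treatment participants across phases and excludes deferred subjects before treatment. SAP Section 1.3.1 already points that way ("by study phases (dose escalation, dose confirmation and expansion phases) and overall, comparing with 6 months data in deferred treatment arm prior to treatment"), but Section 6 does not repeat it.

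The cost is a change of wording and one programming option, with no new data. With 0 to 2 events in groups of 16 or more, the reported upper limits will rise and look less favourable.

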5.5 Outcomes

5.5.1 Primary Outcomes

The primary safety outcome is defined as absence of any of the below occurring during the 9 weeks following administration, at least possibly related to the ATIMP, not surgery alone:

Reduction in visual acuity by 15 ETDRS letters or more

- Severe unresponsive inflammation
- Infective endophthalmitis
- Ocular malignancy
- Grade III or above non-ocular SUSAR (see section 5.11.3)

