2.3.3. Safety Analysis Set

Safety analyses will be performed using the safety analysis set, which includes all immediate treatment subjects (regardless of study phase) who were administered ATIMP, and all deferred subjects who completed their last baseline assessment during the deferred period prior to treatment. Safety analyses will be performed according to actual treatment received.

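### The primary safety outcome is reported for deferred participants before dosing, when it cannot occur, and their own post-dose results are left out of the main estimate

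*SAP*

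**What the plan says.** SAP section 1.3.1 defines the primary safety outcome as any of five listed events "occurring during the 9 weeks following administration, at least possibly related to the ATIMP, not the surgery alone". Protocol section 5.5.1 uses the same two conditions: "occurring during the 9 weeks following administration, at least possibly related to the ATIMP, not surgery alone".

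SAP section 6 gives the proportion with this outcome, and a 95% confidence interval from a continuity-corrected normal approximation. These "will be provided for the immediate treatment subjects and deferred subjects prior to treatment in the safety analysis set". It adds: "The analysis will be performed by study phase, treatment group and overall". For the same deferred participants once dosed, it says only: "The primary safety outcome for all deferred subjects post-treatment will be tabulated separately". A listing of events is also planned.

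The safety analysis set (SAP section 2.3.3) takes in dosed immediate participants and "all deferred subjects who completed their last baseline assessment during the deferred period prior to treatment". Deferred participants thus enter on completing baseline, not on dosing.

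On the comparison, SAP section 1.2 states that "6-month data from deferred arm during deferred period prior to treatment serves as the concurrent control group". Section 1.3.1 says safety in immediate participants will be assessed by phase and overall, "comparing with 6 months data in deferred treatment arm prior to treatment".

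Protocol section 5.10.3.2 gives the purpose of the estimate: an upper limit on the true event rate, through a 95% confidence interval, using safety data from every dose level.

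**The concern.** Safety of the ATIMP is the trial's primary objective, and this outcome is how it is measured. Both conditions in the definition presuppose dosing. Applied to a period before dosing, the outcome returns zero however many participants lose vision or have a serious event. A reader who sees 0% beside the treated rate may take it as a background rate, for example for 15-letter acuity loss in a progressive disease. It carries no such information.

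The period in which deferred participants can have an event is the period the main table omits. The main estimate therefore uses fewer exposed participants than the trial will have. Depending on how the rows are built, it may also use unexposed participants in some denominators.

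**Working it through.** The plan states no event rate, power or precision target for this outcome, and protocol section 5.7 says there is no formal sample size calculation. There is no planned figure to reproduce.

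**Inputs (planned maxima)**
- Dose escalation: 18 (protocol 5.7)
- Paediatric confirmation: 5 (protocol 5.7), or 3 (SAP 1.4)
- Expansion: 16 immediate low, 16 immediate intermediate, 16 deferred, the last split 8 low and 8 intermediate (protocol 5.9.1)
- Check: 18 + 5 + 48 = 71, the protocol total
- True event rate: not in the documents; assumed 5% to 20%

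**1. The pre-treatment row.** No administration means no 9-week window and no possible ATIMP causality, so the count is 0/16 with certainty. The SAP interval is p ± [1.96 × √(p(1−p)/n) + 1/(2n)]. With p = 0 and n = 16 this is 0 ± 1/32, or −3.1% to 3.1%. The exact upper limit would be 20.6%. Neither interval means anything for an event that cannot happen.

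**2. Whether another safety analysis supplies the control comparison.** SAP section 6.1 counts an adverse event as treatment-emergent only from ATIMP administration onward, so its summaries also exclude events in the deferral period.

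**3. Dosed participants outside the main estimate.** 16/71 = 22.5%. Expected events among them are 16 × rate, and the chance of at least one is 1 − (1 − rate)^16:

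| Assumed rate | Expected events | Chance of at least one |
|---|---|---|
| 5% | 0.8 | 56% |
| 10% | 1.6 | 81% |
| 15% | 2.4 | 93% |
| 20% | 3.2 | 97% |

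For these participants' post-treatment efficacy, SAP sections 5.3.3 and 5.4.2 specify estimates with 95% confidence intervals by dose and overall. For the primary safety outcome section 6 specifies neither.

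**4. Conditional: rows that pool undosed deferred participants.** The factor is dosed participants in the row divided by all participants in the row.
- Expansion phase: 32/48 = 0.667
- Overall: (18 + 5 + 32)/(55 + 16) = 55/71 = 0.775
- Overall with the SAP's 3 children: 53/69 = 0.768

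Illustrations, with the SAP's interval method:

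| Events | Dosed immediate only | Upper limit | With undosed deferred added | Upper limit |
|---|---|---|---|---|
| 4 in expansion | 4/32 = 12.5% | 25.5% | 4/48 = 8.3% | 17.2% |
| 6 overall | 6/55 = 10.9% | 20.1% | 6/71 = 8.5% | 15.6% |

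Counting deferred participants from their own dosing also gives denominators of 48 and 71, but then everyone in them is exposed and their events enter the numerator.

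**The case against.** The strongest objection concerns dilution. A reader might infer that the expansion-phase and overall rates will be understated by a third and by 22.5%. The documents do not establish this. Section 6 names two groups without saying they are summed. The full sentence in SAP section 1.3.1 can be read as immediate participants by phase and overall, with the deferred arm as comparator. On that reading the overall row has 55 participants at maxima, all dosed. The table mock-ups are in the Data Presentation Specifications, which are not among the documents and could settle the matter either way. This objection stands: the factors in step 4 are conditional.

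A reader might also infer that deferred post-dose events are lost. They are not; they are tabulated and listed. What is missing is their place in the main proportion and interval.

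No formal test is planned, and section 1.3.1 ties the estimation objective to the escalation phase, which has no deferred arm. That limits the consequences to estimation and interpretation. It does not give the zero row any meaning, and it does not fit easily with the all-dose upper bound in protocol section 5.10.3.2.

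Finally, comparing arms on clinical events regardless of attribution would be a new outcome and would include surgical harm in one arm only. That is correct, so such a table can only be an optional addition.

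**Conclusion.** Two parts hold on the text alone. The pre-treatment deferred row is 0% by construction, so it cannot provide the safety comparison described in SAP section 1.3.1. Up to 16 of 71 dosed participants (22.5%) are outside the main estimate.

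A third part is conditional. If the expansion-phase and overall rows pool undosed deferred participants, those rates are multiplied by 0.667 and by 0.775 (0.768 with 3 children). Sections 6 and 2.3.3 permit that pooling; section 1.3.1 may not intend it.

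On any reading, the rows for the immediate low and intermediate doses and for the escalation and paediatric phases are unaffected. All counts are planned maxima, and the 5% to 20% event rates are assumptions. The SAP is written to protocol v12.0, while the amendment log in the protocol provided ends at v11.0; the outcome definition is the same in both documents, so the conclusion does not depend on the version.

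**What to change.** In SAP section 6:
1. Remove deferred participants before treatment from the primary safety outcome and from every denominator used for it.
2. Give the proportion and 95% confidence interval in all dosed participants by dose, by phase and overall, counting each deferred participant from their own administration day. At maxima the expansion phase then has 16 + 8 = 24 at each dose and 48 in all, and the overall row has 71. Keep the separate deferred post-treatment table as a supporting display.

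Optionally, if a randomised safety contrast is wanted, add a descriptive table of the component clinical events regardless of attribution, over a matched period in both arms, labelled as including the effects of surgery. SAP section 1.3.1 should then point to that table and not to the primary safety outcome.

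The cost is SAP wording and one revised table, with no new data. The reported rate may become less favourable.
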